## **SELECTION OF SUBJECTS**

## ***Eligibility***

### ***For all arms:***

Adults will be eligible to participate if they meet the following criteria:

- Age: ≥18
- Able to read and understand English
- Cognitively able to provide informed consent
- Daily smoker
- Smoke 1-10 cigs/day on average for the last year
- Express a desire to quit smoking in the next 30 days
- Access to a cell phone that can send and receive SMS text messages and take and send pictures

Exclusion criteria for all arms:

- Use (within the past 30 days) of:
  - Psychiatric medications including antidepressants (MAOIs, St. John's Wort), lithium, antipsychotics, or any other medications that are known to affect smoking cessation (e.g. clonidine);
- Current use of:
  - Wellbutrin, bupropion, Zyban, Chantix, varenicline, nicotine patch, nicotine replacement therapy or any other smoking cessation aid;
- Current participation in another smoking study at our Center or another research facility;
- Participated in Duke Smoking Cessation Program in the last year

## **SUBJECT RECRUITMENT & COMPENSATION**

### ***Screening and Recruitment***

We will recruit participants into this low-risk study through Duke Center for Smoking Cessation, Facebook, flyers in public locations, DukeList, Duke Primary Care clinics through the Primary Care Research Consortium, and Durham Public Housing.

Staff will conduct the study in Hock Plaza. When participants call to express interest in a research study, staff will screen them for the study.

At participating clinics in Durham, Wake, Orange, and Chatham counties, with a HIPAA Waiver of Authorization, DHTS will conduct a DEDUCE query to identify potentially eligible patients. We will send patients who report tobacco use of "Light tobacco smoker" and/or "Current everyday smoker" "Smokes some days" a letter from their provider informing them of the study and asking them to call a study phone number if they prefer not to be contacted about study participation. If an email address is accessible for these patients, we may also attempt to email them these documents. We will call or text people who do not call to refuse to screen them for eligibility and set up a screening visit.

The Center for Smoking Cessation and the Nursing School will post Facebook ads through their Facebook accounts. The Facebook ad includes a link to a Qualtrics survey that asks the participant for their contact information. El Centro Hispano staff will refer light smokers to the Qualtrics link as well. Study staff will call those interested people who complete the Qualtrics survey to assess eligibility. The eligibility screening will: confirm a patient's age, smoking status, interest in quitting smoking, use of other tobacco products, pregnancy status, breastfeeding status, and history of serious adverse reaction to cycloserine in the past.

Participants can receive up to \$150 to complete all aspects of the study. Participants will receive \$50 for completion of surveys at Visit 1 and \$100 at the follow-up visit. Participants will not receive

compensation for Visits 2, 3, 4 or 5 as these are intervention visits and we want the motivation to quit smoking to be intrinsic rather than extrinsic. Providing monetary compensation during these intervention sessions can interfere with this.

### **RISK/BENEFIT ASSESSMENT**

Potential risks of study participation include breach of confidentiality with regard to identifiable personal information. Some of the questions participants will be asked might make them feel uncomfortable. All participants may refuse to answer any of the questions and may stop their participation in this study at any time. All of this is outlined in the written consent form the patient signs at the time of enrollment into the study.

Quitting smoking may cause nicotine withdrawal that may lead to headaches, irritability, weight gain, difficulty concentrating, poor sleep, increased appetite, anxious or depressed mood, and craving for cigarettes. Risks associated with drawing blood from the arm include momentary discomfort and/or bruising. Infection, excess bleeding, clotting, or fainting are also possible, although very unlikely.

There may be a direct medical benefit to the participants as they might quit smoking. They also might find the intervention to be helpful. What we learn from the participants in the study will help us develop a P01 grant application being re-submitted to the National Cancer Institute in January 2020.

### **COSTS TO THE SUBJECT**

There will be no additional costs to the participant as a result of being in this study.

### **DATA ANALYSIS & STATISTICAL CONSIDERATIONS**

The purpose of this study is to evaluate the feasibility, acceptability, and preliminary efficacy of an intervention to promote smoking cessation among light smokers. The intervention arms will be compared using descriptive statistics. Results from these analyses will be used to prepare a P01 grant application.

**Statistical Analysis of Feasibility Aim 1:** For this feasibility aim, the two arms will be combined. We have two feasibility metrics. We will consider the intervention feasible if we enroll 6 light smokers per month and 75% complete at least 2 study visits.

**Statistical Analysis of Aim 2:** For this acceptability aim, we will ask participants in all arms how useful the intervention was (1="Not at all useful" to 5="Extremely useful"), whether the intervention will change their smoking (1="Will not change at all" to 5="Will change a lot"), and whether they would recommend the program to a friend (1="Definitely would not recommend" to 5="Definitely would recommend"). For the intervention to be deemed acceptable, 75% of participants in Arm 2 would have to rate each item a "4" or a "5." Note that this decision rule has nothing to do with the efficacy of the control arm. The percentage of participants endorsing "1", "2", "3", "4", and "5" on each of the three Likert-scaled items will be calculated and compared between arms. This comparison will be used to detect any unexpected, gross difference between arms. For example, if arm median on "how useful was the intervention?" were "2" and "5", this result would be considered both unexpected and noteworthy regardless of which arm did better.

**Statistical Analysis of Aims 3 and 4:** This aim will compare the arms on the efficacy of the intervention. We'll start by calculating an estimated prevalence (with 95% confidence interval) for the binary measure of point prevalence, with the confidence interval based on the standard formula for the standard error

or a binomial proportion. We're interested in all 3 pairwise comparisons between the groups, recognizing that only the comparison between groups 1 and 2 is randomized. Each of the comparisons would be based on a chi-square or Fisher's exact test as appropriate. Because this is a pilot study, which is not intended to be a definitive assessment of efficacy all 3 comparisons, we would use a cut-off value of  $p=0.05$  for declaring statistical significance.

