#### ***Specific Aims***

**Aim 1:** To assess the feasibility of an enhanced cue exposure therapy intervention. This aim will specifically address the number of participants recruited and the number of participants who complete all study visits.

**Aim 2:** To evaluate and compare the acceptability of cue exposure therapy compared to standard smoking cessation counseling and support text messages as measured by participants' ratings of the usefulness of the intervention.

**Aim 3:** To compare the preliminary efficacy of an enhanced cue exposure therapy compared to standard smoking cessation and support messages in light smokers as measured by a) self-report 7-day point prevalence abstinence from smoking and b) biochemically validated smoking cessation.

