*Cue exposure therapy measures:* Participants will sit in front of a computer screen while the screen shows a PowerPoint presentation composed of a repeating set of images. Each set will include standardized smoking images and images that have been shown to make people who smoke want to smoke. These images will be from the International Affective Picture System (IAPS), a database of images designed to provide a standardized set of pictures for studying emotion and attention. Also, we plan to use 4-6 of the smoking images that participants have sent themselves. We will only show participants their images, not images taken by other participants. Additionally, participants will also be exposed to in vivo cues by following instructions to touch/hold/smell smoking paraphernalia, including cigarettes, ashtrays, and lighters.

A participant can miss completing any time point/study visit and it is not considered a protocol deviation.

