#### Arm 1 and 2 participants:

After approximately one week, all participants will return for Visit 3. The procedures will be the same as Visit 2, completing the brief smoking assessment and standard smoking cessation counseling. Visit 3 is the last counseling session for Arm 1 participants.

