#### Arm 2 participants:

Participants will also complete cue exposure therapy. This process repeats so participants will come in on a weekly basis for a total of 4 treatment visits (Visits 2, 3, 4, and 5) and will complete the same process as described for Visit 2.

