### Follow-up

For the final visit, participants from all arms will return to the Tobacco Cessation Lab to complete the follow-up assessment. This will occur one week after Visit 5 and one week after Visit 4, respectively. They will complete a questionnaire and we will assess abstinence via 7-day point prevalence.

Participants will provide a saliva sample to biochemically validate their smoking status based on their cotinine levels. At the follow-up visits, we will ask participants if we can contact them after to ask for feedback on the pilot study. If they agree, we will call them or meet them in person to ask for their input.

Participants may also be asked at the time of visits to be audio-recorded for data or quality assurance purposes. They can refuse to be audio-recorded and can still participate in the study.

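### The feasibility rule needs only two undefined study visits in the pooled arms, whereas Aim 1 counts completion of all visits, so its completion criterion can be met although no Arm 2 participant completes the four cue exposure sessions

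*Combined protocol and SAP*

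**What the plan says.** Under Specific Aims, Aim 1 concerns the feasibility of the enhanced cue exposure intervention and is to address "the number of participants recruited and the number of participants who complete all study visits".

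The Statistical Analysis of Feasibility Aim 1 (Data Analysis & Statistical Considerations) sets the decision rule: "We will consider the intervention feasible if we enroll 6 light smokers per month and 75% complete at least 2 study visits". It also says: "For this feasibility aim, the two arms will be combined".

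The visit schedule is spread over several sections:
- Visit 1 is baseline and standard counseling in both arms, without cue exposure (Intervention and Control Activities).
- Arm 2 attends weekly for a "total of 4 treatment visits (Visits 2, 3, 4, and 5"), each with cue exposure.
- For Arm 1, "Visit 3 is the last counseling session for Arm 1 participants".
- All participants return for a follow-up assessment. On its timing: "This will occur one week after Visit 5 and one week after Visit 4, respectively".

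The Data Collection Methods section adds: "A participant can miss completing any time point/study visit and it is not considered a protocol deviation". Subject Recruitment & Compensation pays for Visit 1 and follow-up, and not for Visits 2 to 5.

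For acceptability, the plan judges the intervention arm alone: "For the intervention to be deemed acceptable, 75% of participants in Arm 2 would have to rate each item" at one of the top two scores.

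**The concern.** The aim and the rule that decides it use different measures. The aim counts people who complete everything; the rule asks for any two visits. No section reconciles them, says which visits count, or says whether the 75% is taken of those enrolled, those randomized or those who attended Visit 1.

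The Design section makes feasibility, with acceptability, the primary outcome, and the results are to support a grant application. (Data Collection Methods separately ties the primary outcome to seven-day abstinence. That is a further inconsistency, but it does not change the feasibility rule.) Followed to the letter, the rule could declare a four-session intervention feasible when few of those assigned to it completed it.

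**Working it through.** The 75% is a chosen threshold with no calculation behind it, so there is no derived figure to reproduce. The check is a count of visits, followed by two illustrations.

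**1. What two visits guarantee in Arm 2.** Arm 2 has six visits: Visits 1 to 5 and follow-up. Cue exposure takes place at Visits 2, 3, 4 and 5 only. Listing every pair of counted visits gives the fewest sessions that a participant with exactly two visits can have had:

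| Visits that count | Pair with the least exposure | Sessions guaranteed |
|---|---|---|
| All visits | Visit 1 and follow-up (the two paid visits) | 0 of 4 |
| Visits 1 to 5, without follow-up | Visit 1 and one treatment visit | 1 of 4 |
| Post-baseline only (Visits 2 to 5 and follow-up) | One treatment visit and follow-up | 1 of 4 |
| Treatment visits only (Visits 2 to 5) | Any two treatment visits | 2 of 4 |

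Two visits contain at most two sessions, so no reading requires four. The criterion can read 100% with no Arm 2 participant completing the course.

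**2. Scale under an assumed dropout pattern.** The documents give no retention figure. Assume that everyone attends Visit 1, that a constant share r of those still attending returns for each later visit, that dropout is permanent, and that r is the same in both arms.
- If Visit 1 counts, reaching two visits means attending Visit 2, with probability r. The pass point is r = 0.75. Completing all four sessions has probability r⁴ = 0.75⁴ = 0.316, about 32%.
- If Visit 1 does not count, reaching two visits means attending Visit 3, with probability r². The pass point is r = √0.75 = 0.866. Then r⁴ = 0.75² = 0.5625, about 56%.

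These figures are not a floor. Suppose instead that visits are missed independently, each later visit being attended with probability 0.4, with Visit 1 counted, 1:1 allocation, and three later visits in Arm 1 against five in Arm 2. The pooled share with two visits is [(1 − 0.6³) + (1 − 0.6⁵)]/2 = (0.784 + 0.922)/2 = 0.853, which passes. The share of Arm 2 attending all four sessions is 0.4⁴ = 0.026, about 3%.

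**3. Pooling.** No allocation ratio is stated. At an assumed 1:1, the pooled rate is the mean of the two arms' rates. If 95% of Arm 1 reaches two visits, Arm 2 needs only 2 × 75% − 95% = 55%. If Arm 1 is at 100%, Arm 2 needs (0.75 − 0.5)/0.5 = 50%. The same formula gives 25% if Arm 2 is one third of the sample and 62.5% if it is two thirds. Under the equal retention of step 2, both arms have the same two-visit rate and pooling changes nothing.

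**4. Arm 1's visit list.** The Visit 3 section ends Arm 1's counseling at Visit 3. The Follow-up section times follow-up only from Visit 5 or Visit 4. So it is unclear whether Arm 1 has a Visit 4, and with it what completing all visits means in that arm.

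**The case against.** The best defence is that the two sections do different jobs. Aim 1 names a quantity to address and sets no threshold; the analysis section holds the only stated rule. A pilot may choose a tolerant bar, and the protocol expects missed visits, since it does not treat them as deviations. If only treatment visits count, two is also the whole of Arm 1's post-baseline counseling (Visits 2 and 3), so the rule could be meant as a floor common to both arms, which would fit with pooling.

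Some of this stands. A lenient threshold is the sponsor's to choose, and moving the criterion to all visits would not be an obvious improvement: it would ask six visits of Arm 2 but four of Arm 1 as described, and would fail someone who attended every session and missed only follow-up. But the common-floor reading is inference, since the plan does not state it, and it still leaves Arm 2 at two of four sessions.

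Three stronger readings are tempting and are not supported:
- A reader might infer that the rule can pass with no cue exposure delivered at all. That holds only if Visit 1 and follow-up both count, and only if people skip Visits 2 to 5 and then return. It cannot arise under the permanent dropout assumed in step 2.
- A reader might infer that pooling necessarily hides poor Arm 2 attendance. It does so only if Arm 2 attends worse than Arm 1.
- A reader might infer that completion will go unreported. The all-visits count is itself an Aim 1 measure and the arms are to be compared descriptively, so low completion could still be seen.

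The enrollment condition of six per month must also be met, but it says nothing about completion.

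**Conclusion.** The point holds for the completion criterion. Aim 1 and its decision rule disagree, the counted visits and the denominator are undefined, and on no reading does the rule require the four-session course that defines the intervention. This follows from the text alone.

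The 32% and 56% rest on assumed constant, permanent and equal dropout after Visit 1. They show scale and are not forecasts, and the documents give no reason to expect that nobody would complete. Pooling is a secondary and conditional weakness. The consequence is that a primary outcome may carry a misleading label into the grant application; no data are lost. This should be fixed, but it does not invalidate the trial.

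**What to change.** Before looking at the data:

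1. State which visits count in each arm and the denominator of the percentage (for example, all randomized participants). Reconcile the Visit 3 and Follow-up sections on Arm 1's visits and the timing of its follow-up.
2. Reconcile Aim 1 with the decision rule by basing the intervention-feasibility criterion on cue exposure sessions attended (Visits 2 to 5) in Arm 2, with a threshold that the sponsor sets and justifies. The Aim 2 rule already judges Arm 2 alone.
3. Report the distribution of sessions attended (0 to 4) in Arm 2, with an exact 95% confidence interval for the proportion completing. Report follow-up attendance and the all-visits count by arm as separate lines, so that a missed follow-up is not read as abandoned treatment.
4. Keep recruitment pooled, and keep the pooled two-visit figure as descriptive.

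The cost is a few sentences, using attendance data the trial already has. The downside is a stricter bar and a wider interval from using one arm. No sample size is stated; for an assumed 15 of 20 completing, the exact 95% interval is 51% to 91%.

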## Project Q Pilot

### PURPOSE OF THE STUDY

The purpose of this pilot study is to evaluate the feasibility, acceptability, and preliminary efficacy of an intervention to promote smoking cessation among light daily and intermittent smokers. The intervention will include a combination of cognitive-behavioral cessation counseling and cue exposure treatment. This pilot study aims to test tailored intervention strategies for light smokers. We will use data from this pilot as preliminary data for a P01 grant application we will resubmit to the National Cancer Institute in January 2020.

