Thus, effective cessation programs for light smokers need to incorporate traditional cognitive strategies that promote self-regulation, behavioral learning strategies to optimize the ability to unlearn smoking cues, and elements to increase motivation, decrease barriers, increase self-efficacy and improve outcome expectations.

In this small, randomized controlled pilot trial, we will test the feasibility, acceptability, and preliminary efficacy of a combination of cognitive behavioral cessation counseling and cue exposure treatment, a cue driven treatment that has been found effective in the treatment of substance use. Further, we will extend cue exposure therapy beyond the clinic or laboratory by using interactive texting to help light smokers transfer their newly learned cue extinction skills into their natural environment. Interactive

texting will include both self-monitoring and extinction of cue extinction skills. Interactive texting for real-time data collection will include participants taking photographs of cues they identify as salient and triggering of their desire to smoke as well as texting when they smoke and their craving levels. We will incorporate the participants own photographs into their tailored cue exposure treatment conducted in the clinic

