### **DESIGN & PROCEDURES**

#### ***Design***

The two-arm trial compares Arm 1) standard smoking cessation counseling and 2) enhanced cue exposure treatment. For all arms, we will conduct a phone screening, provide smoking cessation counseling, and an in-person follow-up visit. The primary outcome will be feasibility and acceptability. The secondary outcome will be biochemically-validated cessation 1-week post-intervention.

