#### ***Data Collection Methods***

For all arms:

The baseline survey will include questions about demographics, smoking factors, and household information. The follow-up surveys will include some of the same questions as the baseline as well as process questions to assess helpfulness of the messages and participants' fidelity to the intervention protocol. The primary outcome will be assessed using seven-day point prevalence abstinence (e.g., Have you smoked any cigarettes in the past 7 days?) and biochemically validated through saliva analysis.

***Saliva samples:*** Saliva samples from participants at baseline and follow-up will be used to biochemically validate the participant's smoking status. NicAlert strips will be used to measure the cotinine levels in the saliva at baseline and follow-up.

***Text-message real-time data collection:*** We will ask participants in Arm 2 to text study staff every time they smoke and every time they have a strong urge to smoke for four consecutive days. The system will ask participants to rate their level of craving (1-10) and stress (1-10) via text. We will also ask participants in Arm 2 to take and text several photos of the situation in which they smoked/had the urge to smoke. Additionally, we will ask all participants to text the system every time they feel like smoking or

have an urge to smoke between Visits 2 and the follow-up visit. The system will ask the same questions about craving and stress but participants will not be asked to text a photo. For Arm 2 participants, the system will reply with a supportive message to encourage the participant not to smoke along with the questions. Participants will be instructed not to text while driving and only to text when it is safe to do so.

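### The planned 95% interval for abstinence is the Wald interval with no small-sample alternative: it collapses to 0%–0% with no quitters and its upper limit is too low with few

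*Combined protocol and SAP*

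**What the plan says.** The paragraph on Aims 3 and 4 in Data Analysis & Statistical Considerations begins the efficacy analysis by "calculating an estimated prevalence (with 95% confidence interval) for the binary measure of point prevalence". The rest of that sentence fixes how the limits are to be obtained: "with the confidence interval based on the standard formula for the standard error". The parameter it then names is a binomial proportion. (The sentence crosses a page break and prints *or* where *of* is evidently meant.) No other interval is named, and there is no rule for zero or few quitters.

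The one allowance for sparse data concerns the tests: "Each of the comparisons would be based on a chi-square or Fisher's exact test as appropriate".

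The measure is the first efficacy outcome under Aim 3 in Specific Aims: "self-report 7-day point prevalence abstinence from smoking". Its rank is stated in two ways. The Design section says "The primary outcome will be feasibility and acceptability"; Data Collection Methods says "The primary outcome will be assessed using seven-day point prevalence abstinence".

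The background describes the study with the words "In this small, randomized controlled pilot trial". The document gives no total or per-arm sample size, no recruitment duration and no expected quit rate.

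**The concern.** An estimate plus or minus 1.96 standard errors, with the standard error taken from the observed proportion, is the Wald interval. It performs poorly when counts are small or the proportion is near 0 or 1, and a small cessation pilot may well produce such counts. The standard error is zero when nobody quits, so the formula then reports certainty from an absence of events. With a few quitters the interval is centred too low and is too short on the upper side.

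What is at stake is reporting. The Purpose section says "We will use data from this pilot as preliminary data for a P01 grant application", and this is the only interval planned for efficacy. An upper limit that is too low hides quit rates that the data do not exclude. Replacing the method after seeing the counts would be an unplanned deviation.

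**Working it through.** **Inputs.** From the plan: a binary outcome, 95% confidence (taken as two-sided, so z = 1.96 and z² = 3.8415), and the standard-error formula. Assumed, because the plan is silent: n = 10 to 50 per arm and true abstinence of 5% to 50%. The plan contains no worked interval to reproduce.

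**Formulas**, for x quitters out of n and p̂ = x/n:

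- Wald: p̂ ± z√(p̂(1−p̂)/n)
- Wilson: [p̂ + z²/(2n) ± z√(p̂(1−p̂)/n + z²/(4n²))] / (1 + z²/n)

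**Step 1: no quitters (no quit rate assumed).** With x = 0, Wald has standard error 0 and gives 0%–0% at every n. The Wilson upper limit reduces to z²/(n + z²); for n = 20 this is 3.8415/23.8415 = 16.1%. For n = 10, 15, 20, 30, 40 and 50 it is 27.8%, 20.4%, 16.1%, 11.4%, 8.8% and 7.1%.

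**Step 2: few quitters (no quit rate assumed).** The Wald lower limit is negative when x < z²(1 − x/n), that is, when x < 3.8415 and n > 3.8415x/(3.8415 − x). The bounds are n > 1.35 for x = 1, n > 4.17 for x = 2 and n > 13.70 for x = 3. So it is negative with one quitter from n = 2, two from n = 5 and three from n = 14, and never with four or more.

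| Quitters | Wald | Wilson |
|---|---|---|
| 1/20 | −4.6% to 14.6% | 0.9% to 23.6% |
| 2/20 | −3.1% to 23.1% | 2.8% to 30.1% |
| 3/20 | −0.6% to 30.6% | 5.2% to 36.0% |

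For 1/20, the Wald half-width is 1.96 × √(0.05 × 0.95/20) = 1.96 × 0.0487 = 9.6 points around 5%.

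**Step 3: coverage over assumed values.** Coverage is the exact binomial probability of all x whose interval contains the true rate. Wald coverage (%) of the nominal 95% interval:

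| n per arm | 5% | 10% | 15% | 20% | 30% | 40% | 50% |
|---|---|---|---|---|---|---|---|
| 10 | 40.0 | 65.0 | 79.3 | 88.6 | 84.0 | 89.9 | 89.1 |
| 15 | 53.6 | 79.2 | 89.6 | 81.5 | 94.9 | 93.9 | 88.2 |
| 20 | 63.9 | 87.6 | 81.9 | 92.1 | 94.7 | 92.8 | 95.9 |
| 30 | 78.2 | 80.9 | 94.2 | 94.6 | 95.3 | 93.5 | 95.7 |
| 40 | 86.8 | 91.4 | 93.9 | 90.5 | 93.0 | 94.6 | 91.9 |
| 50 | 92.0 | 87.9 | 94.1 | 93.8 | 93.5 | 94.1 | 93.5 |

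Wald is below 90% in 19 of 42 cells: 15 of 21 at n = 10–20, and 4 of 21 at n = 30–50, all four at 5–10% abstinence. Coverage does not rise smoothly with n or the rate, so the table draws no sharp boundary. Over the same cells Wilson runs from 91.4% to 98.2% and Clopper-Pearson from 95.7% to 99.5%.

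**Step 4: direction of the misses.** Probability that the Wald upper limit is below the truth, against the lower limit being above it:

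- n = 20, 10% abstinence: 12.2% against 0.2%
- n = 20, 15%: 17.6% against 0.6%
- n = 15, 20%: 16.7% against 1.8%
- n = 30, 10%: 18.4% against 0.8%

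**Step 5: chance of a 0%–0% interval.** This is (1 − p)ⁿ for true rate p. At 10% and 20% abstinence it is 35% and 11% for n = 10, 21% and 3.5% for n = 15, 12% and 1.2% for n = 20, and 4.2% and 0.1% for n = 30.

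**The case against.** The practical effect depends on two quantities that the plan does not give. If the arms have 30 or more participants and abstinence is 15% or higher, tabulated Wald coverage is 90.5–95.7% and little is lost; the very low values come only from small arms with low quit rates. This stands, and it is why the coverage figures are illustrations over a range. Steps 1 and 2 do not depend on it.

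A negative lower limit is largely cosmetic: an analyst would print 0, and with three quitters in 20 it is only −0.6%. This also stands. But truncating at zero repairs neither the 0%–0% interval nor the low upper limit, which are the substantive faults.

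No decision rests on the interval. The feasibility and acceptability rules do not use it, sparse counts are provided for in the tests, and the plan says the pilot is not a definitive assessment of efficacy. That supports a low rating. It does not make the stated formula suitable, since in a pilot the interval is the main expression of how little is known.

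Finally, the same paragraph refers to a fourth aim and to three pairwise comparisons, while the rest of the document has three aims and two arms. Changing the interval method does not settle that; it needs its own correction. The conflict over which outcome is primary is likewise separate and does not alter this point.

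**Conclusion.** The concern holds and is minor. Followed as written, the plan reports 0%–0% for any arm without quitters, and with few quitters its upper limit is too low: 14.6% rather than 23.6% at 1/20. These results follow from the formula alone. The loss of coverage, down to 40.0% in the worst tabulated cell, rests on assumed values of n and the quit rate; at n ≥ 20 with abstinence of 20% or more, tabulated coverage is 90.5–95.9% and the choice matters little. The conclusion rests on reading the standard formula as the Wald interval. The document does not use that name, but this is the natural reading.

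**What to change.** In the Aims 3 and 4 paragraph, replace the standard-error clause with wording such as: *with a 95% confidence interval for each arm calculated by the Wilson score method*. Clopper-Pearson is an acceptable alternative if coverage of at least 95% is wanted.

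The cost is one phrase; design, conduct and data are unaffected, and both methods are in standard software. Intervals become asymmetric, and wider when quitters are few. At 10% abstinence the expected width, Wilson against Wald, is 37 against 28 points at n = 10, 30 against 26 at n = 15 and 26 against 23 at n = 20. From 20% abstinence upward Wilson is about equal or narrower (37 against 38 at n = 15 and 20%). Clopper-Pearson is wider: 34 points at n = 15 and 10%.

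### The efficacy paragraph plans three pairwise comparisons in a two-arm trial, uses an error-prone per-arm interval at low counts, and plans no interval for the arm difference

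*Combined protocol and SAP*

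**What the plan says.** The Design section states: "The two-arm trial compares Arm 1) standard smoking cessation counseling and 2) enhanced cue exposure treatment". The Randomization section allocates every participant to one of those two arms. Specific Aims lists three aims. The third compares the arms on "self-report 7-day point prevalence abstinence from smoking and b) biochemically validated smoking cessation". Design adds: "The secondary outcome will be biochemically-validated cessation 1-week post-intervention".

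The efficacy paragraph in Data Analysis & Statistical Considerations is headed for Aims 3 and 4. It starts by "calculating an estimated prevalence (with 95% confidence interval) for the binary measure of point prevalence". The interval is the usual one for a single binomial proportion, built from its standard error. The paragraph then says the team is "interested in all 3 pairwise comparisons between the groups, recognizing that only the comparison between groups 1 and 2 is randomized". Each comparison is a chi-square or Fisher test with a 0.05 cut-off. The paragraph gives no interval for a difference or a ratio between arms.

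In the same section, the Aim 1 text says "For this feasibility aim, the two arms will be combined", and the opening says "Results from these analyses will be used to prepare a P01 grant application".

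**The concern.** The paragraph describes a set of comparisons that does not match the trial. Three pairs need three groups, and by the paragraph's own account one of them is outside the randomisation. No such group is described anywhere, and there is no Aim 4. Anyone reporting against this plan must either explain two missing tests or decide unaided what the third group was.

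Two matters of estimation come with it. The per-arm interval relies on a normal approximation that breaks down when few participants are abstinent, as can happen in a small pilot. And the quantity Aim 3 is about, the difference between arms, gets a p-value but no statement of its uncertainty. If the results go into a grant application in that form, readers could see falsely narrow per-arm intervals and no interval on the effect.

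**Working it through.** **1. Number of comparisons.** With g groups there are g(g-1)/2 pairs.

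- The plan's figure of 3 requires g = 3, since 3 x 2 / 2 = 3.
- Design, Randomization and the Aim 1 analysis text all give g = 2, so 2 x 1 / 2 = 1.
- The plan's figure is not reproduced: 3 - 1 = 2 comparisons have no defined group.

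Native versus converted smoking status does not supply the missing group. In the Randomization section it is a stratification factor within the two arms.

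**2. The planned per-arm interval.** The documents give no sample size, so 20 per arm is an assumption. I read the planned formula as p +/- 1.96 x sqrt(p(1-p)/n).

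- 0/20: 0 +/- 1.96 x 0, which is 0% to 0%.
- 2/20: 0.10 +/- 1.96 x sqrt(0.09/20) = 0.10 +/- 0.131, which is -3.1% to 23.1%.

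The Wilson interval has centre (p + z²/2n)/(1 + z²/n) and half-width z x sqrt(p(1-p)/n + z²/4n²)/(1 + z²/n), with z² = 3.84.

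- 0/20: 0.0806 +/- 0.0806, which is 0% to 16.1%.
- 2/20: 0.1644 +/- 0.1366, which is 2.8% to 30.1%.

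The planned formula also gives a negative lower limit for 1, 2 or 3 abstainers at each of 15, 20 and 30 per arm.

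**3. Coverage.** For an assumed true rate, coverage is the sum of the binomial probabilities of the counts whose interval contains that rate. At n = 20 and a true 5%, the planned interval contains 5% only for counts 1 to 4: 0.377 + 0.189 + 0.060 + 0.013 = 0.639. The main loss is the count 0, with probability 0.95^20 = 0.36.

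| Assumed true rate | Planned, n=15 | Planned, n=20 | Planned, n=30 | Wilson, n=20 |
|---|---|---|---|---|
| 5% | 53.6% | 63.9% | 78.2% | 92.5% |
| 10% | 79.2% | 87.6% | 80.9% | 95.7% |
| 20% | 81.5% | 92.1% | 94.6% | 95.6% |

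Across these rates and all three sizes Wilson covers 92.5% to 98.2%. At true rates of 30% to 40% the planned formula covers 92.8% to 95.3% and Wilson 91.5% to 97.5%, and neither is uniformly better. At 15 per arm and 30%, the planned formula covers about 95% and Wilson 91.5%.

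**4. What an interval for the difference would show.** Assume 2/20 in Arm 1 and 6/20 in Arm 2, so d = 0.30 - 0.10 = 0.20. The Wilson limits are 0.028 to 0.301 and 0.145 to 0.519. The Newcombe limits are:

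- Lower: 0.20 - sqrt((0.300 - 0.145)² + (0.301 - 0.100)²) = 0.20 - 0.254 = -0.054.
- Upper: 0.20 + sqrt((0.519 - 0.300)² + (0.100 - 0.028)²) = 0.20 + 0.231 = 0.431.

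That is +20 points, 95% interval -5 to +43, with a Fisher p-value of 0.24. Enumerating all two-arm tables, the expected full width of this interval, from 5% versus 10% up to 20% versus 40% abstinent, is 47.6 to 58.5 points at 15 per arm, 39.9 to 51.7 at 20, and 31.2 to 43.1 at 30.

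**The case against.** The best defence is that the one comparison that matters is fully usable. The paragraph names groups 1 and 2 as the randomised pair and gives the test and the cut-off. The other two comparisons drop out for want of a group, and no result for Arm 2 versus Arm 1 changes. This stands. A reader might infer that the whole written analysis cannot be run. The text does not support that; two of the three comparisons cannot be.

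A reader might also infer a family-wise error of 1 - 0.95³ = 14.3% from three tests at 0.05. That does not follow either, because only one of the three can be carried out.

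On the outcome, the paragraph names only point prevalence, and a reader might infer that validated cessation was left out of the analysis. Data Collection Methods ties point prevalence to saliva validation, and Follow-up collects both at one visit, so the paragraph can be read with those sections. Because Specific Aims lists the two measures separately, naming both would help, but this is a matter of drafting.

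On intervals, the section says the arms will be compared descriptively and that the pilot is not a definitive efficacy test. Any reader given the counts could compute the difference and its interval. The case for Wilson also depends on low abstinence rates, which the documents do not predict. These points limit the weight of the criticism. They do not rescue a 0% to 0% interval, and they do not explain why a paragraph that attaches a significance cut-off to the comparison attaches no uncertainty to its size.

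**Conclusion.** The point holds in a limited form and should be corrected. Three parts rest on the documents alone: two of three planned comparisons have no defined group, the heading cites an aim that does not exist, and no interval is planned for the arm difference. The behaviour of the planned per-arm formula at 0 abstainers (zero width) is a property of the formula at any sample size.

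The coverage and width figures are illustrations at assumed sizes of 15 to 30 per arm and assumed rates. They show that the planned interval can cover far less than 95% at true rates of 5% to 10%. They do not show that it will do so in this trial, and the advantage of Wilson is not consistent at 30% to 40%.

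Efficacy is not the primary outcome in the Design section. The feasibility and acceptability rules do not use this paragraph, so those decisions are unaffected.

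**What to change.** Head the paragraph Aim 3, and remove the Aim 4 and three-comparison wording. If a third group is intended, define it and report it descriptively, without significance claims. Suggested text:

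> One randomised comparison, Arm 2 minus Arm 1, is made at the follow-up visit for (a) self-reported 7-day abstinence and (b) biochemically validated cessation. For each measure we report n/N and prevalence per arm with a 95% Wilson interval, and the risk difference with a 95% Newcombe interval. The chi-square or Fisher p-value is supportive.

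Naming both measures is a clarification of wording. The cost is one paragraph and no new data, plus a definition if a third group exists. The drawback is that the intervals will be wide and will show openly how little a pilot of this kind can say about efficacy.
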